BRCA2	Breast Cancer Gene Type 2
CA	Competent Authority
CI	Chief Investigator
CRF	Case Report Form
EPCAM	Epithelial cell adhesion molecule
EC	Endometrial Cancer
EQ-5D	EuroQol 5-dimensional questionnaire
GAFREC	Governance Arrange for NHS Research Ethics Committees
GCP	Good Clinical Practice
GDPR	General Data Protection Regulation
HRQL	Health-Related Quality of Life
HRUS	Health-Related Utility Scores
ICF	Informed Consent Form
LNG-IUS	Levonorgestrel Intrauterine System
LS	Lynch Syndrome
MLH1	MutL homolog 1
MSH2	MutS homolog 2
MSH6	MutS homolog 6
NHS REC	National Health Service Research Ethics Committee
NHS R&D	National Health Service Research & Development
OC	Ovarian Cancer
PMS2	Post Meiotic Segregation increased 2
PI	Principle Investigator
PIS	Participant Information Sheet
QALY	Quality Adjusted Life Year
REC	Research Ethics Committee
RRS	Risk Reducing Surgery
RRH	Risk Reducing hysterectomy
RRHBSO	Risk Reducing hysterectomy and bilateral salpingo-oophorectomy
SAE	Serious Adverse Events
SDV	Source Document Verification
SOP	Standard Operating Procedure
SNP	Single Polynucleotide
SSA	Site Specific Assessment
TMG	Trial Management Group

3. Signature page

CI Agreement

The study, as detailed within this Research Protocol, will be conducted in accordance with the principles of Good Clinical Practice (GCP), the UK Policy Framework for Health and Social Care Research, and the Declaration of Helsinki and any other applicable regulations. I agree to take responsibility for the statistical analysis and oversight of this study.

CI Name:

[name]

[name]

Signature:

Date:

10/1/24

4. Summary and synopsis

Short title	PRESCORES
Methodology	Cross-sectional cohort study, questionnaire-based
Objectives / aims	 To determine who would benefit from preventive strategies for Endometrial Cancer: To determine the health-related utility scores for risk reducing hysterectomy for endometrial cancer To determine the lifetime risk thresholds of Endometrial Cancer for cost-effectiveness of preventive interventions To determine the acceptability of preventive strategies for endometrial cancer in the general population
Number of	Not applicable
participants	
Inclusion and exclusion criteria	 Inclusion criteria: Part 1: a) Female b) Age ≥18 years old c) Lynch Syndrome diagnosis - confirmed germline mutation in MLH1, MSH2, MSH6, PSM2, ECPAM d) UK Resident Exclusion criteria: Part 1: a) Unwilling or unable to provide informed consent b) Inability to understand written and verbal English c) Prior history of endometrial, ovarian or cervical cancer
Statistical methodology and analysis (if applicable)	Baseline characteristics will be calculated with descriptive statistics. Appropriate regression analysis & cohort matched analysis will be used to evaluate impact of covariates on categorical and linear variables. Decision analysis using Markov model for health- economic analysis.
Study duration	36 months

5. Introduction

5.1. Background

Endometrial cancer and prevention

Endometrial cancer (EC) is the fourth commonest women's cancer in the UK with ~9300 cases each year(1-3) This incidence is predicted to rise by 25.4% in the UK, and 52.7% globally by 2040(4). Reproductive and lifestyle factors which increase oestrogen exposure are acknowledged to influence carcinogenesis (5), including obesity, diabetes mellitus, early menarche, nulliparity and Tamoxifen use. However, 2-5% of EC arise in the context of a hereditary cancer syndrome(6-8).

Lynch Syndrome (LS) affects an estimated 1 in 280-370 people (9, 10), and is responsible for around 3% of EC cases (7, 8, 11). It is caused by an autosomal dominant inherited pathogenic variant (PV) or likely pathogenic variant (here forth called pathogenic variant or PV) in the DNA mismatch-repair (MMR) genes (*MLH1, MSH2, MSH6, PMS2, EPCAM*), and is the commonest inheritable cause of EC. This results in a lifetime risk of EC of 13-57% (12-14), depending on the mismatch repair gene involved. EC is often described as the 'sentinel' cancer in LS women (13, 15, 16). However, LS also results in an increased lifetime risk of ovarian cancer (OC) of up to 17% (14, 17), and predisposes to colorectal cancer as well as cancers of the stomach, hepatobiliary, urinary tract and brain (13).

Management of LS is primarily focused on reducing cancer risk. For LS associated gynaecological cancers, screening programmes are not yet nationally available as a clear impact on mortality remains to be demonstrated (18, 19). Therefore, access remains dependent on involvement in a research trial and/or geographical location.

Risk-reducing surgery is the most clinically effective intervention to prevent EC and OC in women with LS, with no cases of EC and only a few case reports of primary peritoneal cancer found following this.(18, 20) Risk reducing surgery involves risk-reducing hysterectomy (RRH) for endometrial cancer prevention, with bilateral salpingo-oophorectomy (BSO) to remove the fallopian tubes and ovaries, for OC prevention.

The decision making process for risk reducing surgery for LS is complex and dynamic, and changes with time. It may be affected by a number of factors including age, cancer history, fertility wishes, menopausal status and other considerations. Whilst the decision for surgery is often motivated by a desire to reduce cancer worry and risk (21), RRH results in a definitive end to fertility and can raise complex psychosocial concerns surrounding femininity (22). Any operation has risks of perioperative complications, and a recovery period. Pre-menopausal bilateral oophorectomy, for women at increased risk of OC, leads to an abrupt oestrogen withdrawal and premature menopause. This is associated with significant sequelae such as vasomotor symptoms and an adverse impact on libido and sexual function (23, 24), as well as longer-term risks of osteoporosis, coronary heart disease, cognitive impairment and dementia, Parkinsonism, and detrimental impact on quality

of life (25-30). These effects are greater in women who have RRH-BSO under the age of 45-50 years and who don't take Hormone Replacement Therapy. Different women will have different priorities in choosing whether and when to have risk-reducing surgery (31).

Health Economic Disutility Analysis

The impact of RRH with or without BSO for EC prevention upon Health-Related Quality of Life (HRQoL) remains unknown. HRQoL is defined as a subjective perception of the impact of health status, including disease and treatment, on a person's physical, psychological and social functioning (32). Although this measure is primarily based on patient experiences, objectively quantifying these figures allows comparisons within disease cohorts and more broadly across different health-care interventions. Health-Related Utility Scores (HRUS) represent an objective measures of a health state, by assigning a value of between 0 (death) and 1 (perfect health) to each condition.

The UK's National Institute for Health and Care Excellence (NICE) recommends economic decision models should use HRUS to calculate guality-adjusted life years (QALYs) (33). In their guidance on the evaluation of health technologies, NICE recommends such models be based upon the "reference case", to ensure a consistent approach to health-economic modelling across multiple diseases and technologies (34-36). The preferred instrument is the EQ-5D; a generic patientreported-outcome measure developed by the EuroQol Group, which assesses quality of life using five domains; mobility, self-care, usual activities, pain/ discomfort, anxiety/depression (37). This questionnaire was originally available with three levels of response for each domain (known as EQ-5D-3L), although a version with fivelevels of response has been developed, allowing for finer discrepancy between health states (known as EQ-5D-5L, hereafter referred to as EQ-5D) (38). EQ-5D ratings are converted to HRUS using a country-specific formula, derived from a timetrade-off exercise conducted on a representative sample of the general population for each country (39). Thus the "reference case" provides for patient-reported outcomes to be converted to HRUS using the valuations of society.

Understanding the impact of RRH-BSO on HRQoL would enable clinicians to better support women with increased EC risk contemplating risk-reducing surgery in a complex decision making process. Additionally, the derivation of HRUS would enable more accurate health-economic and cost-effectiveness analysis of risk reducing surgery to prevent EC. Disutility is a key variable and driver which can affect the results of these analysis. It is currently unknown what level of lifetime EC risk would justify risk-reducing treatments, although such modelling has been undertaken for risk-reducing BSO in OC prevention (40, 41).

The aim of this research would be to obtain HRUS for pre and post-menopausal patients undergoing RRH for EC prevention. This can then be used to build decision analysis models to define the EC lifetime risk threshold at which to perform RRH.

5.2. Rationale

The major benefit of this modelling is that it would be relevant for any condition which raises EC lifetime risk, which includes not only LS, but any number of potential genetic or lifestyle risk factors. This includes women with mutations in *PTEN* tumour suppressor genes, who have a lifetime EC risk of 19-28% (42). This may also in the future include women with model based risk estimation or potentially women heterozygous for *BRCA1* PVs. While some studies suggest an increased risk of serous EC relative to the low-risk population (43) (44, 45) (46), in *BRCA1* women, the overall data on serous EC risk are inconsistent, with some studies showing no increase in risk,(47) and overall EC-risk is not increased. While not currently recommended in most guidelines, internationally and even within the UK, there is some inconsistency in international clinical practice with respect to offering a RRH in combination with risk reducing BSO in *BRCA1* women.

The need for multiple parts

This modelling requires accurate HRUS for risk-reducing surgery for EC. Ideally, the impact of EC prevention on quality-of-life would be considered in isolation, without additional disutility from screening or prevention of other cancers (such as ovarian or colorectal cancer), or of an early surgical menopause for pre-menopausal patients. Opportunistic bilateral salpingectomy is commonly performed with hysterectomy to provide some degree of OC risk reduction, even in a low-risk population (48). There is no evidence that bilateral salpingectomy with RRH reduces hormonal function or quality-of-life over that of RRH alone (49), and therefore no requirement to consider the impact of bilateral salpingectomy separately from RRH. Bilateral oophorectomy with RRH for post-menopausal women would not be expected to add to the disutility of RRH alone. The major distinction therefore lies in pre-menopausal patients, and whether bilateral oophorectomy is performed with RRH.

Our target population from which to obtain EQ-5D ratings would therefore be:

- 1) **Pre-menopausal** women undergoing RRH for EC risk-reduction, with bilateral oophorectomy.
- 2) **Pre-menopausal** women undergoing RRH for EC risk-reduction, **without** bilateral oophorectomy
- 3) **Post-menopausa**l women undergoing RRH for EC risk-reduction, with or without bilateral oophorectomy.

RRH without bilateral oophorectomy is not commonly performed, as national guidelines recommend that women with LS have RRH-BSO to protect them from their additional OC risk (50) (51). There may be a small number of LS women who have received RRH alone without bilateral oophorectomy outside of recommended practice. Whilst these women would be valuable in obtaining HRUS for this procedure, they would be expected to have some additional risk of anxiety from their remaining risk of ovarian and colorectal cancer. Whilst there are numerous risk factors for EC, few patients other than those with LS undergo RRH (52), and so there is no major cohort of patients who have received RRH alone (for cancer prevention) without bilateral oophorectomy, and who are now free from an elevated risk of any other cancer.

Due to the rarity of this target patient cohort, it is challenging to perform a prospective EQ-5D study for patients undergoing this procedure. Where EQ-5D ratings are not available for a specific treatment or condition, due to rarity or other factors, NICE recommends alternatives, including the use of the closest available "proxy conditions", and vignettes (36, 53). People with LS represent the best available target patient population for the development of HRUS for EC preventive surgery. However, it is necessary to use a separate methodology for pre-menopausal patients undergoing RRH without bilateral oophorectomy. A preferred study design is the development of vignettes describing the treatment and condition of interest, which is then rated using EQ-5D by the general population or patients with similarities to the condition. This provides the closest match to the NICE reference case (54).

This study will therefore obtain EQ-5D ratings of risk reducing surgery for endometrial cancer via two related approaches:

- A cross-sectional EQ-5D study of women with LS, including those who have undergone RRH ± BSO and those who have not (controls). This will enable HRUS for RRH to be obtained, including for pre and post-menopausal patients undergoing RRH-BSO.
- 2) A vignette-based study of pre-menopausal RRH without bilateral oophorectomy (for a patient with no remaining cancer risk). This will be valued by members of the general population using EQ-5D ratings.

Acceptability of risk-reducing strategies

Prior to clinical utilisation, it is necessary to determine if risk-reducing surgery is acceptable to women in the target population.

Acceptability has been defined by Sekhon and colleagues as "the extent to which people delivering or receiving a healthcare intervention consider it to be appropriate, based on anticipated or experienced cognitive and emotional responses to the intervention" (55). These authors described seven component constructs, which can be measured before (prospectively), during (concurrently), or after the delivery of the intervention (retrospectively) (56): Affective attitude (how the patient feels about the procedure), burden (the expected amount of effort required to undergo the procedure), intervention coherence (the extent to which the patient understands why the procedure is being done), ethicality (how the procedure fits with the patient's values or beliefs), opportunity costs (the costs involved in undergoing the procedure, and recovering), perceived effectiveness (the extent to which the patient believes the procedure will achieve its aims), and self-efficacy (the confidence a patient has in being able to complete the procedure).

The acceptability of an intervention is distinct from the experience of that service, which may be affected by factors such as the quality of facilities, waiting times, transport links and others (57).

A recent study highlights initial data on willingness of obese women at increased risk of EC to undergo non-surgical primary preventive interventions to reduce EC risk.(58) Data also exist on acceptability of diet and lifestyle interventions in EC survivors.(59)

However, to the best of our knowledge, no previous studies have examined the acceptability of risk-reducing hysterectomy for EC prevention (outside the context of women with LS) at various EC risk levels. For ovarian cancer prevention, risk reducing salpingo-oophorectomy has been shown to be acceptable to a large proportion of women in the general population at the 5% level of absolute lifetime risk (60). Other studies have demonstrated risk-reducing early-salpingectomy followed by delayed oophorectomy to be acceptable to women at high risk of ovarian cancer (61, 62). We intend to assess the prospective acceptability of RRH to the general population, for EC prevention at differing levels of lifetime absolute risk of EC.

This study has scope to influence clinical practice for all patients with elevated risk of EC by defining the risk threshold at which to offer RRH and determining the acceptability of preventive surgery at that risk level. This study conforms to the methodological considerations of NICE, and will be directly applicable to health-economic and cost-effectiveness analyses of preventive treatments for endometrial cancer.

This study will address a number of **knowledge gaps** regarding endometrial cancer prevention:

- EQ-5D ratings of risk-reducing hysterectomy for endometrial cancer prevention, with separate ratings for:
 - Pre-menopausal risk-reducing hysterectomy with bilateral salpingooophorectomy
 - Pre-menopausal risk-reducing hysterectomy without bilateral salpingooophorectomy
 - Post-menopausal risk-reducing hysterectomy with bilateral salpingooophorectomy
- The lifetime endometrial cancer risk-threshold at which risk reducing surgery and other strategies are cost-effective
- The prospective acceptability of risk-reducing strategies for endometrial cancer prevention for women in the general population

5.3. Risks / benefits

Benefits

Participants in this study are unlikely to gain immediate benefit from participation, except for the satisfaction of having contributed to this study on endometrial cancer prevention.

Participants in this study may benefit, along with women in the wider population, from the knowledge gained from this study, if they are at elevated endometrial cancer risk. If successful, this study will demonstrate the endometrial cancer lifetime risk at which prevention strategies could be adopted, which will pave the way for their consideration by national commissioning bodies such as NICE.

Risks

There are few risks to participants in this questionnaire-based study, involving the completion of only one questionnaire per participant at a single time point.

Potential participants may not wish to complete the study. All participants will have ample opportunity to read the relevant participant information sheet (PIS), before giving voluntary written informed consent, should they choose to participate. Participation in the study is entirely voluntary and will not in any way affect their medical care, and this will be emphasised during the consent process.

Some participants may find it difficult to complete the questionnaires, due to the sensitive or personal nature of some questions (focusing on cancer risk and prevention). Participants will be told that participation is entirely voluntary, and they are free to either not continue or withdraw from the study at any time, without giving a reason. Information about support from charities such as Lynch Syndrome UK will be provided in the PIS.

6. Study objectives

6.1. Primary objective

• To obtain health-related utility scores for risk-reducing hysterectomy for endometrial cancer prevention

6.2. Secondary objectives

- To determine variables predictive for risk reducing hysterectomy
- To determine separate health-related utility scores for pre and postmenopausal patients undergoing risk-reducing hysterectomy with and without ovarian conservation.
- To define the endometrial cancer risk threshold for undergoing risk-reducing hysterectomy
- To determine the cost-effectiveness of risk-reducing hysterectomy
- To establish whether risk-reducing hysterectomy and other preventive options are acceptable to women in the general population at differing levels of lifetime risk of endometrial cancer
- To determine variables predictive of acceptability of risk-reducing hysterectomy

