7.4. Questionnaire structure

7.4.1. Study Part-1: Questionnaire 1 Structure

Paper/electronic questionnaires will be identical, and participants will be required to complete one format of the questionnaire of their choosing. The questionnaire will be completed at one-time point, to reflect the cross-sectional study design. Upon completion there will be no further responsibilities.

Questionnaires will contain the following sections;

- Lynch Syndrome and health
- EQ-5D-5L questionnaire (63, 64) for participants' current HRQoL
 - Consists of two sections: EQ-5D-5L descriptive system and the visual analogue scale. It has five dimensions: mobility, self-care, activities of daily living, pain and mood disturbance. Participants are asked to indicate their health state on a five-point Likert scale.
- EQ-5D-5L questionnaire (63, 64) for participants' HRQoL 4 months after their RRH (for participants who have undergone RRH)
- Cancer Worry Scale (65)
 - The 4 items of the CWS are rated on a 4-point Likert scale ranging from "never" to "almost always." Scores range from 4 to 16. Higher scores indicate more frequent worries about cancer (66). The Cancer

Worry Score has been validated for use in Hereditary Cancer Syndrome Context with a Cronbach-alpha from 0.88 to 0.89 (66).

- Medical and family history
- Demographic information

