8.1. Inclusion criteria

Part 1:

- Diagnosis of Lynch Syndrome (confirmed germline mutation in *MLH1*, *MSH2*, *MSH6*, *PSM2*, *EPCAM*)
- ≥18 years
- Female
- UK resident
- Able and willing to provide informed consent

For part 1, eligible participants will be adult women with LS living in the UK. This is to reflect the full range of views and experiences from this group, including from different age groups.

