9.7. Follow-up Procedures

There will be no follow-up for any participant in any part of the study. Upon completion of the relevant questionnaire (and return of the consent form and questionnaire for those completing on paper), there will be no further involvement in the study.

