10.2. Method of analysis

Baseline characteristics will be calculated using descriptive statistics. Appropriate statistical tests will be used. Chi-square tests will be used to compare categorical

variables and t-Test (parametric) and Mann-Whitney (non-parametric) tests to compare continuous outcome variables between two groups. Appropriate Logistic/ Linear regression models will be used to evaluate impact of covariates on Linear outcome variables. The data set will be subject to two analysis formats to minimise the risk of bias during interpretation. Initially by cohort-matching, to reduce the influence of confounding variables. Secondly by regression analysis to analyse the impact of covariates of the categorical and linear variables. All analysis will be performed on R (R Core Team, Foundation for Statistical Computing, Vienna, Austria), or equivalent software package.

A Markov model built in TreeAge software (TreeAge, Williamstown, MA) will form the basis of an economic evaluation on the cost-effectiveness of RRH for endometrial cancer risk threshold at which to perform surgical prevention (hysterectomy) or other non-surgical preventive interventions (such as the levonorgestrel-intrauterine system, or other chemo-prevention) for endometrial cancer risk. Models will be built in order to evaluate lifetime costs as well as effects with undertaking 'risk reducing hysterectomy' in premenopausal and postmenopausal women by comparing it with 'no risk reducing hysterectomy' at varying levels of endometrial cancer risk. Additional modelling will also evaluate lifetime costs as well as effects as well as effects of endometrial cancer risk. Additional modelling will also evaluate lifetime costs as well as effects of endometrial cancer risk. Additional modelling will also evaluate lifetime costs as well as effects of endometrial cancer risk. Additional modelling will also evaluate lifetime costs as well as effects with undertaking non-surgical preventive interventions in premenopausal and postmenopausal women by comparing it with 'no intervention' at varying levels of endometrial cancer risk. The analysis will be undertaken primarily within the UK National Health Service (NHS) context. We will also explore the impact of outcomes in other health systems.

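### Predictors of risk-reducing hysterectomy (RRH) are promised from one survey, taken after surgery in every RRH woman, with no named method that accounts for time at risk

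*Protocol*

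**What the plan says.** Protocol 6.2 lists "To determine variables predictive for risk reducing hysterectomy" among the secondary objectives, and 6.4 lists the same item first among the secondary endpoints.

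The data source is Questionnaire 1 in Part 1. Section 7.4.1 says "The questionnaire will be completed at one-time point, to reflect the cross-sectional study design", and 9.7 adds "There will be no follow-up for any participant in any part of the study". Section 8.1 admits women with LS from age 18, with no minimum time since diagnosis: "This is to reflect the full range of views and experiences from this group, including from different age groups". Section 5.2 calls the women without RRH controls.

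The instruments listed in 7.4.1 are EQ-5D-5L for current health, a second EQ-5D-5L recalled for 4 months after RRH, and one Cancer Worry Scale. None is anchored before surgery. Medical and family history and demographics are also collected, but the items are not shown.

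Section 10.2 names chi-square, t and Mann-Whitney tests, cohort matching and regression: "Appropriate Logistic/ Linear regression models will be used to evaluate impact of covariates on Linear outcome variables". It gives no outcome coding, time origin or covariate list for this objective.

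Section 5.1 describes the decision itself: "The decision making process for risk reducing surgery for LS is complex and dynamic, and changes with time". It also says: "Whilst the decision for surgery is often motivated by a desire to reduce cancer worry and risk".

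**The concern.** Two features of the design work against the word predictive.

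**Time at risk.** RRH accumulates over the years after an LS diagnosis. At survey, a woman without RRH may have declined it or may not yet have reached the decision. A comparison by RRH status at survey counts both the same way. Any covariate that goes with longer or shorter time since diagnosis then picks up an association with RRH, even if it plays no part in the choice. Adjusting for current age does not settle this, because two women of the same age can have been diagnosed many years apart.

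**Order of measurement.** In every woman with RRH, the current worry and EQ-5D scores are post-operative. By the protocol's own account, surgery is often sought in order to lower worry. A current score therefore mixes what led to surgery with what surgery changed.

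At stake is a named secondary endpoint that could report predictors which are not predictors, or give the wrong direction for cancer worry.

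**Working it through.** The protocol gives no figure for this objective. The only protocol number used below is the 30% with RRH in 10.1. All rates, durations and shifts are assumptions chosen for illustration, and nothing is adjusted for.

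**1. Time since diagnosis, closed form.** Assume the same constant uptake rate *h* per year for everyone, so the true rate ratio is 1. The proportion with RRH after *t* years is P = 1 − exp(−*ht*), the odds are exp(*ht*) − 1, and the odds ratio (OR) is [exp(*ht*₁) − 1] / [exp(*ht*₂) − 1].

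| Uptake per year | Years since diagnosis | Ever RRH | OR |
|---|---|---|---|
| 5% | 20 v 5 | 63.2% v 22.1% | 1.718/0.284 = 6.05 |
| 5% | 15 v 10 | 52.8% v 39.3% | 1.117/0.649 = 1.72 |
| 2% | 20 v 5 | 33.0% v 9.5% | 0.492/0.105 = 4.68 |
| 2% | 15 v 10 | 25.9% v 18.1% | 0.350/0.221 = 1.58 |

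These compare groups separated entirely by time since diagnosis. A covariate only partly linked to that time would show less.

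**2. A null covariate, by simulation at 30% ever RRH.** Two equal groups differ in mean time since diagnosis but have the same uptake rate.

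- Mean 3 v 6 years: 22% v 38% ever RRH, OR 0.46.
- Mean 3 v 9 years: OR 0.30.
- Mean 2 v 10 years: OR 0.17.

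The ratio of events per person-year stays at 1.00 to 1.01 in all three. For 3 v 6 years, an unadjusted two-sided 5% test would declare a predictor about 100% of the time with 750 respondents and 86% of the time with 300 (the desirable number and the lower limit in 10.1).

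**3. Cancer worry.** If women choosing surgery were 0.3 SD more worried beforehand and surgery lowers worry by 0.5 SD, the survey shows 0.3 − 0.5 = −0.2 SD, so they appear less worried. In a logistic simulation at 30% RRH, the OR per SD of worry at survey is:

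| True pre-surgery OR | Fall 0.25 SD | Fall 0.5 SD | Fall 0.75 SD | Fall 1 SD |
|---|---|---|---|---|
| 1.3 | 1.00 | 0.78 | 0.61 | 0.47 |
| 1.5 | 1.17 | 0.90 | 0.68 | 0.53 |
| 2.0 | 1.51 | 1.16 | 0.89 | 0.67 |

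With no fall after surgery, the true OR is recovered (1.31, 1.49 and 2.02). The direction reverses once the fall is large relative to the initial difference.

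**The case against.** The strongest reply is that the protocol does not contain the analysis being criticised. It never says that RRH is coded ever/never, that women without RRH are treated as decliners, or that worry, EQ-5D or menopausal status enters a predictor model. EQ-5D is there for the utility scores, and the word controls appears in a passage about EQ-5D ratings. Matching and covariate regression are planned, and nothing shows that time since diagnosis would be left out. Model details for a secondary objective commonly sit in a statistical analysis plan (SAP), which may exist unseen.

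Much of this stands. A reader might also infer that most unoperated women are simply too young or too recently diagnosed; the documents give no distribution of age or time since diagnosis, so that is not shown. Nor do they show that menopausal status is recorded only as it is now: 6.2 asks for separate utilities for pre- and post-menopausal women undergoing RRH, which needs status at surgery. A Cox model is not the only remedy, since discrete-time logistic regression also handles duration.

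Two things remain. None of the methods named in 10.2 accounts for time at risk unless it is added, and an SAP can add it only if the relevant ages are collected, which the protocol does not show. And no SAP can recover pre-surgery worry or quality of life that the listed instruments do not measure.

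**Conclusion.** The point holds in a limited form. The objective promises predictors, while the one-time survey and the methods named in 10.2 do not support that word for covariates that track time since LS diagnosis or for scores measured after surgery. The first part depends on RRH status at survey being the outcome, which is the natural reading but is inferred. The second applies if current worry or EQ-5D is offered as a predictor. MMR gene is not altered by surgery, but any fixed variable that goes with time since diagnosis remains exposed to the first problem.

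The size cannot be fixed from the documents. Under the assumed rates, and with no adjustment, spurious odds ratios run from 1.6 to 6.0. The upper value should not be read as the expected bias, because it comes from an extreme contrast that good control for time since diagnosis would remove. The reversal for worry rests on assumed shifts.

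This should be corrected, but it concerns a secondary endpoint. Nothing in 10.2 feeds it into the utility scores or the economic model.

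**What to change.** - **Data.** Confirm that Questionnaire 1 records age at LS diagnosis and age at RRH, and add them if it does not.
- **Analysis.** In 10.2, state that uptake of RRH will be analysed with time at risk taken into account: time from LS diagnosis to RRH with censoring at survey, or discrete-time logistic regression.
- **Predictors.** Restrict the term to variables fixed or dated before RRH, such as gene and family history, and parity and menopausal status at surgery if recorded.
- **Current scores.** Report current cancer worry and EQ-5D as post-surgery associations.
- **Limitation.** State that 8.2 excludes women with prior endometrial, ovarian or cervical cancer. Unoperated women who developed one of these cancers are therefore missing, and the risk set is selected. Modelling time at risk does not cure this.

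The cost is a change of wording, possibly two questionnaire items, and some variables no longer being called predictors. The ages are easiest to secure before data collection ends.
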